### **Overall survival**

OS is defined as the time from the date of the first dose of study treatment to the date of death due to any cause.

### **Changes in platelet count, hemoglobin and neutrophil count**

Value and changes in platelet count (in the absence of platelet transfusion), hemoglobin (in the absence of RBC transfusion) and neutrophil count (in the absence of G-CSF) will be calculated according to the lab test results entered into CRF.

## **2.7.2 Statistical hypothesis, model, and method of analysis**

### **CR rate at Week 13, Week 52 and yearly after**

The number and percentage of subjects who meet the hematological CR criteria (at Week 13, Week 52 and yearly after respectively) will be presented and 2-sided Exact binomial 95% ([Clopper-Pearson](#)) confidence interval will be reported.

### **Overall response (CR+PR) rate at Week 13, Week 26, Week 52 and yearly after**

The number and percentage of subjects who meet the hematological overall response criteria (at Week 13, Week 26, Week 52 and yearly after respectively) will be presented and 2-sided Exact binomial 95% ([Clopper-Pearson](#)) confidence interval will be reported.

The overall response rate will also be summarized by the above subgroups listed in [section 2.2.1](#) for efficacy.

Hematological response endpoints will be listed based on the investigator assessment and the programmatic derivation.

### **Time to response**

The Kaplan-Meier curve of the time to response and time to complete response will be constructed, and the quartiles of the survival function will be provided along with 95% confidence interval. Kaplan-Meier estimates with 95% confidence intervals every 3 months will be summarized as well.

### **Duration of response**

Kaplan-Meier curve of the duration of response and duration of complete response will be constructed, and the quartiles of the survival function will be provided along with 95% confidence interval. Kaplan-Meier estimates with 95% confidence intervals every 3 months will be summarized as well.

### **Transfusion-free interval before Week 13 and Week 26**

Descriptive statistics including mean, SD, median, 25th and 75th percentiles, minimum, and maximum will be summarized for the transfusion-free interval. The same analysis applies to RBC transfusion.

#### **Maximum duration of Platelet and RBC transfusion free**

Maximum duration of platelet and RBC transfusion free will be summarized by descriptive statistics including mean, SD, median, 25th and 75th percentiles, minimum, and maximum separately.

#### **Proportion of subjects who becomes transfusion independent**

The number and percentage of subjects with platelet or RBC transfusion independence at any time during the study will be presented respectively.

#### **Transfusion frequency and amount**

The frequency and the amount of platelets and RBC transfusion in each period will be summarized by descriptive statistics including mean, SD, median, 25th and 75th percentiles, minimum, and maximum.

The number and percentage of subjects with platelet or RBC transfusion decrease and 50% platelet transfusion reduction in each period will be presented.

#### **Overall survival**

Kaplan-Meier curve of the OS will be constructed, and the quartiles of the survival function will be provided along with 95% confidence interval. OS rate will be estimated at Week 26, Week 52 and yearly after as well.

#### **Changes in platelet count, hemoglobin and neutrophil count**

Values and changes in platelet count (in the absence of platelet transfusion), hemoglobin (in the absence of RBC transfusion) and neutrophil count (in the absence of G-CSF) will be summarized at each visit. Descriptive statistics including mean, SD, median, 25th and 75th percentiles, minimum, and maximum will be summarized for the changes. Median and interquartile range will be plotted.

### **2.7.3 Handling of missing values/censoring/discontinuations**

#### **CR rate at Week 13, Week 52 and yearly after**

For the analysis CR, patients who are still ongoing but have not reached the considered timepoint yet will not be included in the analysis of response at that timepoint. Subjects who are not evaluable for response at specific visit for any reason, including missing data and withdrawal from the study before specific visit, will be treated as non-responders in the analysis.

#### **Overall response (CR+PR) rate at Week 13, Week 26, Week 52 and yearly after**

For the analysis overall response, patients who are still ongoing but have not reached the considered timepoint yet will not be included in the analysis of response at that timepoint. Subjects who are not evaluable for response at specific visit for any reason, including missing

data and withdrawal from the study before specific visit, will be treated as non-responders in the analysis.

### **Time to response**

For time to response and time to complete response, if a subject does not meet response/CR before or at the cutoff date, censoring will be performed using the date of the last response assessment.

### **Duration of response**

Patients who are neither complete nor partial responders will not be included in the analysis of the duration of response. Complete and partial responders who did not relapse at the data cut-off date will be censored at the date of the last assessment of response with a known outcome.

Patients who are not complete responders will not be included in the analysis of the duration of complete response. Complete responders who did not change to PR or relapse at the data cut-off date will be censored at the date of the last assessment of response with a known outcome.

### **Transfusion-free interval before Week 13 and Week 26**

For platelet transfusion, only subjects with response assessments at specific visits (Week 13 or 26) are included in the transfusion-free interval. The same rule applies to RBC transfusion.

### **Maximum duration of Platelet and RBC transfusion free**

This analysis will be only performed for the subgroup of subjects with baseline transfusion dependent.

### **Proportion of subjects who becomes transfusion independent**

This analysis will be only performed for the subgroup of subjects with baseline transfusion dependent.

### **Transfusion frequency and amount**

The transfusion frequency and amount and the proportion of subjects with transfusion decrease will be only performed for the subgroup of subjects with baseline transfusion dependent.

### **Overall survival**

Analysis of overall survival will be based on the FAS. If a subject is not known to have died, survival will be censored at the date of last contact.

## **2.8 Safety analyses**

For all safety analyses, the safety set will be used. All listings and tables will be presented for all subjects.

Safety summaries (tables, figures) include only data from the on-treatment period with the exception of baseline data which will also be summarized where appropriate (e.g., change from baseline summaries). In addition, a separate summary for death including on treatment and post treatment deaths will be provided. In particular, summary tables for AEs will summarize only on-treatment events, with a start date during the on-treatment period (treatment-emergent AEs).

The on-treatment period lasts from the date of first administration of study treatment to 30 days after the date of the last actual administration of eltrombopag.

## **2.8.1 Adverse events (AEs)**

### **Coding and grading**

Adverse events will be coded using the Medical dictionary for regulatory activities (MedDRA) Terminology and their severity assessed according to the Common Terminology Criteria for Adverse Events (CTCAE) version 4.03.

### **General rules for AE Reporting**

AE summaries will include all AEs occurring during on treatment period. All AEs collected in the AE (e)CRF page will be listed along with the information collected on those AEs e.g. AE relationship to study drug, AE outcome etc. AEs with start date outside of on-treatment period will be flagged in the listings.

AEs will be summarized by number and percentage of subjects having at least one AE, having at least one AE in each primary system organ class (SOC) and for each preferred term (PT) using MedDRA coding. A subject with multiple occurrences of an AE will be counted only once in the respective AE category. A subject with multiple CTCAE grades for the same preferred term will be summarized under the maximum CTCAE grade recorded for the event. AE with missing CTCAE grade will be included in the 'All grades' column of the summary tables.

In AE summaries, the primary system organ class will be presented alphabetically and the preferred terms will be sorted within primary SOC in descending frequency. The sort order for the preferred term will be based on their frequency.

The following adverse event summaries will be produced for AEs occurring during the on-treatment period; overview of adverse events and deaths, AEs by SOC and PT, summarized by maximum CTCAE grade, summarized by relationship (all AEs and AEs related to eltrombopag), seriousness (SAEs and non-SAEs), leading to treatment discontinuation, leading to dose interruption/changes, requiring additional therapy and leading to fatal outcome. Specifically, CTC grade  $\geq 3$  adverse events will be summarized for AEs by SOC and PT.

Furthermore, AE occurring during the on-treatment period will be summarized by subgroup summarized by the above subgroups listed in [section 2.2.1](#). These summaries include: AEs by SOC and PT, AEs with suspected relationship to eltrombopag by SOC and PT and SAEs by SOC and PT.

In addition, on treatment adverse events will be summarized by SOC and PT and by periods (by  $\leq 30$  days,  $>30$  to  $\leq 90$  days,  $>90$  to  $\leq 180$  days,  $>180$  to  $\leq 360$  days). Time of onset of first episode will be used when experiencing the same episode in a subject.

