6.1 Study treatment

The investigational drug for this study is eltrombopag (ETB115). The study treatment includes eltrombopag, r-ATG and CsA.

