9.2 Study completion and post-study treatment

Study completion is defined as when the last participant finishes her/his Study Completion visit, and any repeat assessments associated with this visit have been documented and followed-up appropriately by the Investigator, or in the event of an early study termination decision, the date of that decision.

All treated participants should have a safety follow-up visit conducted 30 days after last administration of eltrombopag. The information collected is kept as source documentation. All SAEs reported during this time period must be reported as described in [Section 10.1.3](#). Documentation of attempts to contact the participant should be recorded in the source documentation.

The primary analysis will be performed after all participants have completed Week 26 or discontinued prior to Week 26. The primary analysis data will be summarized in the primary clinical study report (CSR). Following the cut-off date for the analysis reported in the primary CSR, the study will remain open. Ongoing participants will continue to receive study treatment and be followed as per the schedule of assessments, as long as participants derive benefit from eltrombopag.

The end of study defined as the earliest occurrence of one of the following:

1. All participants have died or discontinued from the study or complete the study participation per protocol.
2. Another clinical study becomes available that can continue to provide eltrombopag in this participant population and all participants ongoing are eligible to be transferred to that clinical study.

At the end of Year 2 in this study, participants who in the opinion of the Investigator are still deriving clinical benefit from further CsA treatment should be directed by the treating physician to receive the product through commercial channels locally. The final analysis will occur at the end of the study. All available data from all participants up to this cut-off date will be analyzed and summarized in a final CSR.

10 Safety monitoring and reporting

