10.1 Definition of adverse events and reporting requirements

10.1.1 Adverse events

An adverse event (AE) is any untoward medical occurrence (e.g. any unfavorable and unintended sign [including abnormal laboratory findings], symptom or disease) in a participant or clinical investigation participant after providing written informed consent for participation in the study. Therefore, an AE may or may not be temporally or causally associated with the use of a medicinal (investigational) product.

The investigator has the responsibility for managing the safety of individual participant and identifying AEs.

Novartis qualified medical personnel will be readily available to advise on trial related medical questions or problems.

The occurrence of AEs must be sought by non-directive questioning of the participant at each visit during the study. AEs also may be detected when they are volunteered by the participant during or between visits or through physical examination findings, laboratory test findings, or other assessments.

Once the study ICF is signed, all AEs per the descriptions below will be captured in the Adverse Event CRF.

AEs must be recorded under the signs, symptoms, or diagnosis associated with them, accompanied by the following information (as far as possible) (if the event is serious refer to [Section 10.1.2](#)):

1. The Common Toxicity Criteria (CTC) AE grade (version 4.03). Grade 1 to 5 will be used to characterize the severity of the AE. AE will be assessed and graded according to the Common Terminology Criteria for Adverse Events (CTCAE) version. All grade 4 or higher value on Laboratory/investigational finding will be considered a medically significant event. Details of CTCAE Grade 5 and Fatal AEs will be recorded on Death page in eCRF.
2. its relationship to the investigational drug and other investigational treatment. If the event is due to lack of efficacy or progression of underlying illness (i.e. progression of the study indication) the assessment of causality will usually be 'Not suspected.' The rationale for this guidance is that the symptoms of a lack of efficacy or progression of underlying illness are not caused by the trial drug, they happen in spite of its administration and/or both lack of efficacy and progression of underlying disease can only be evaluated meaningfully by an analysis of cohorts, not on a single participant

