12.5.2 Safety endpoints

For all safety analyses, the safety set will be used. All listings and tables will be presented for all participants.

Safety summaries (tables, figures) include only data from the on-treatment period with the exception of baseline data which will also be summarized where appropriate (e.g., change from baseline summaries). In addition, a separate summary for death including on treatment and post

treatment deaths will be provided. In particular, summary tables for AEs will summarize only on-treatment events, with a start date during the on-treatment period (treatment-emergent AEs).

The overall observation period will be divided into three mutually exclusive segments:

1. Pre-treatment period: from day of participant's informed consent to the day before first dose of study treatment.
2. On-treatment period: from date of first administration of study treatment to 30 days after date of last administration of eltrombopag.
3. Post-treatment period: starting at day 30+1 after last dose of eltrombopag

Adverse events

All information obtained on AEs will be displayed by participant.

The number (and percentage) of participants with treatment emergent AEs (events started after the first dose of investigational drug or events present prior to start of study treatment but increased in severity based on preferred term) will be summarized in the following ways:

- by treatment, primary system organ class and preferred term.
- by treatment, primary system organ class, preferred term and maximum CTCAE severity.

Separate summaries will be provided for investigational drug (eltrombopag) related AEs, death, SAEs, other significant AEs leading to discontinuation, and AEs leading to dose modification.

The number (and proportion) of participants with AEs of special interest will be summarized.

A participant with multiple AE within a primary system organ class is only counted once towards the total of the primary system organ class.

AEs which will be counted for a specific treatment period are those which are treatment-emergent. These events are those with an onset after the start of the treatment period, or which were present prior to the start of the treatment period but increased in severity, changed from being not suspected to being suspected of investigational drug relationship, or developed into SAEs after the start of the treatment period.

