Summary tables for AEs will include only AEs that started or worsened during the on-treatment period, the **treatment-emergent** AEs.

The incidence of treatment-emergent AEs (new or worsening from baseline) will be summarized by system organ class and or preferred term, severity (based on CTCAE grades), type of AE, relation to study treatment.

SAEs, non-serious AEs and AESI during the on-treatment period will be tabulated.

All deaths (on-treatment and post-treatment) will be summarized.

All AEs, deaths, and SAEs (including those from the pre- and post-treatment periods) will be listed and those collected during the pre-treatment and post-treatment period will be flagged.

Vital signs

All vital signs data will be listed by participant, and visit/time and if ranges are available, abnormalities will be flagged. Summary statistics will be provided by treatment and visit/time.

12-lead ECG

PR, QRS, QT, QTcF and RR intervals will be obtained from 12-lead ECGs for each participant during the study.

Shift tables of ECG findings ('Normal' or 'Abnormal') from baseline to worst on-treatment result will be generated. Descriptive statistics at baseline, one or several post-baseline time points and change from baseline to this/these post-baseline time points will be presented.

ECG evaluations for all participants with at least 1 abnormality will be listed. All ECG data will be listed by participant and visit/time, abnormalities will be flagged.

Clinical laboratory evaluations

All laboratory data will be listed by participant and visit/time and if normal ranges are available, abnormalities will be flagged. Summary statistics will be provided by treatment and visit/time. Shift tables using CTCAE grades or the low/normal/high/ (low and high) classification will be used to compare baseline to the worst on-treatment value.

Grading of laboratory values will be assigned programmatically as per NCI Common Terminology Criteria for Adverse Events (CTCAE), version 4.03. The calculation of CTCAE grades will be based on the observed laboratory values only, clinical assessments will not be taken into account.

CTCAE Grade 0 will be assigned for all non-missing values not graded as 1 or higher. Grade 5 will not be used.

For laboratory tests where grades are not defined by CTCAE, results will be categorized as low/normal/high based on laboratory normal ranges.

The following summaries will be generated separately for hematology, and biochemistry tests:

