#### **General rules for AE Reporting**

AE summaries will include all AEs occurring during on treatment period. All AEs collected in the AE (e)CRF page will be listed along with the information collected on those AEs e.g. AE relationship to study drug, AE outcome etc. AEs with start date outside of on-treatment period will be flagged in the listings.

AEs will be summarized by number and percentage of subjects having at least one AE, having at least one AE in each primary system organ class (SOC) and for each preferred term (PT) using MedDRA coding. A subject with multiple occurrences of an AE will be counted only once in the respective AE category. A subject with multiple CTCAE grades for the same preferred term will be summarized under the maximum CTCAE grade recorded for the event. AE with missing CTCAE grade will be included in the 'All grades' column of the summary tables.

In AE summaries, the primary system organ class will be presented alphabetically and the preferred terms will be sorted within primary SOC in descending frequency. The sort order for the preferred term will be based on their frequency.

The following adverse event summaries will be produced for AEs occurring during the on-treatment period; overview of adverse events and deaths, AEs by SOC and PT, summarized by maximum CTCAE grade, summarized by relationship (all AEs and AEs related to eltrombopag/CsA/r-ATG), seriousness (SAEs and non-SAEs), leading to treatment discontinuation, leading to dose interruption/changes, requiring additional therapy and leading to fatal outcome. Specifically, CTC grade  $\geq 3$  adverse events will be summarized for AEs by SOC and PT.

Furthermore, AE occurring during the on-treatment period will be summarized by subgroup summarized by the above subgroups listed in [section 2.2.1](#). These summaries include: AEs by SOC and PT, AEs with suspected relationship to eltrombopag by SOC and PT and SAEs by SOC and PT.

In addition, on treatment adverse events will be summarized by SOC and PT and by periods (by  $\leq 30$  days,  $>30$  to  $\leq 90$  days,  $>90$  to  $\leq 180$  days,  $>180$  to  $\leq 360$  days). Time of onset of first episode will be used when experiencing the same episode in a subject.

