#### **Study treatment**

Study treatment includes any of the following: r-ATG, CsA, eltrombopag or combination of these drugs administered to the patient as part of the required study procedures up to the end of Year 2.

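### The final-analysis SAP tabulates related adverse events for eltrombopag only and drops the protocol's summary by relation to the three-drug study treatment

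*SAP*

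**What the plan says.** The SAP file holds two plans: one for the primary analysis (last dated 1-Jul-2022) and one for the final analysis (11-Nov-2024). Both deal with adverse event tables in Section 2.8.1, General rules for AE Reporting.

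- **Protocol 12.5.2, first statement:** "Separate summaries will be provided for investigational drug (eltrombopag) related AEs".
- **Protocol 12.5.2, second statement:** the incidence of treatment-emergent events "will be summarized by system organ class and or preferred term, severity (based on CTCAE grades), type of AE, relation to study treatment".
- **Meaning of study treatment:** Protocol 6.1 says "The study treatment includes eltrombopag, r-ATG and CsA". The general definitions in the final SAP (2.1.1) agree: "Study treatment includes any of the following: r-ATG, CsA, eltrombopag or combination of these drugs".
- **Causality data:** under Protocol 10.1.1 the investigator records for each event "its relationship to the investigational drug and other investigational treatment".
- **Primary-analysis SAP 2.8.1:** events are "summarized by relationship (all AEs and AEs related to eltrombopag/CsA/r-ATG), seriousness (SAEs and non-SAEs").
- **Final-analysis SAP 2.8.1:** events are "summarized by relationship (all AEs and AEs related to eltrombopag), seriousness (SAEs and non-SAEs").
- **Scope of the final report, Protocol 9.2:** "All available data from all participants up to this cut-off date will be analyzed and summarized in a final CSR".

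**The concern.** The safety objective in Table 1-1 is about eltrombopag given together with r-ATG and CsA, not eltrombopag alone. If the final SAP is followed as written, the only related-event summary in the final report covers one drug of the three. An on-treatment event that the investigator attributes to CsA or r-ATG but not to eltrombopag is then missing from every related-event table in that report.

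The cut is also silent. The final SAP says openly that it drops subgroups (2.2.1), unchanged baseline tables (2.3), the primary endpoint analyses (2.5), secondary endpoints up to Week 26 (2.7) and PK (2.9). It does not mention this removal. Section 4, on changes to the protocol's analyses, lists only added efficacy endpoints, and the document history describes the plan as a first version. A reader comparing the final report with the protocol would find a missing summary and no explanation.

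**Working it through.** The plan states no figure on this point, so the main check compares the texts.

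**Which relationship summaries are required, and which are planned?**

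| Source | Eltrombopag-related | Related to study treatment (three drugs) |
|---|---|---|
| Protocol 12.5.2 | required | required |
| Primary-analysis SAP 2.8.1 | planned | planned |
| Final-analysis SAP 2.8.1 | planned | absent |

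No other part of the final SAP plans a table of events related to study treatment, to CsA or to r-ATG. The relationship does appear in the listing of all adverse events, but a listing is not the incidence summary that 12.5.2 asks for.

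**Is study treatment just loose wording for eltrombopag?** No. Amendment 3 set out to end that ambiguity. It fixed the term as the three-drug combination and also edited 12.5.2. The current 12.5.2 still uses both terms, one in each statement. The primary-analysis SAP keeps them apart as well: its safety subgroups (2.2.1) refer to relationship to study treatment and/or eltrombopag.

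**How much on-treatment time would the primary report's table already cover?** The documents give no accrual curve, so only a range is possible. Assumptions: enrolment or first visit is Day 1; the primary cut-off is the earliest possible; all 36 participants have the maximum on-treatment time of 365 + 30 = 395 days.

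- Last patient first visit was 03-Dec-2021, so that participant's Day 183 is 03-Jun-2022, taken as the cut-off.
- Three participants were enrolled by 08-Dec-2020 and are fully covered: 3 × 395 = 1,185 days.
- The other 33 entered over the 360 days up to 03-Dec-2021. A participant who started t days before that date has min(395, 183 + t) days covered, which is complete once t reaches 395 − 183 = 212.
- Uniform accrual: mean covered time = [183 × 212 + 212²/2 + (360 − 212) × 395] / 360 = (38,796 + 22,472 + 58,460) / 360 = 332.6 days. Share = (33 × 332.6 + 1,185) / (36 × 395) = 12,160 / 14,220, about 86%.
- Extreme case, all 33 starting on the last day: (33 × 183 + 1,185) / 14,220 = 7,224 / 14,220, about 51%.

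On these assumptions, roughly 14% to 49% of on-treatment person-time falls after the primary cut-off. Non-responders at Week 26 stop treatment then, so the remainder lies mainly with responders in the extension part.

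**How far would the restored table reach?** On-treatment time ends 30 days after the last eltrombopag dose (final SAP 2.8). Take a responder assumed to stay on CsA to Year 2 (Day 729 in Protocol Table 8-1).

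- Eltrombopag to Week 52: 365 + 30 = Day 395, and 395/729 = 54% of the CsA period.
- Earliest taper under Protocol Table 6-4 (halved at Week 26, interrupted 8 weeks later, never restarted): 183 + 56 = Day 239, then 239 + 30 = Day 269, and 269/729 = 37%.

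These two percentages describe the limit of the remedy. They do not measure what the omission loses.

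**The case against.** The strongest reply has four parts.

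1. **The table is planned once already.** Protocol 12.5.2 names the summary without saying it must be run at both analyses, and the primary-analysis SAP says it also supports the final analysis. Its introduction and the final SAP's share the sentence about describing all planned analyses, so that sentence alone cannot show that one plan displaces the other. This has some force, but it does not close the gap. Adverse event tables are not among the outputs the final SAP says will not be reproduced; they are re-run on all data to the final cut-off, as Protocol 9.2 expects. The later plan, specific to the final analysis, rewrites this very sentence.
2. **The protocol wording is loose.** The second statement in 12.5.2 fixes no table layout and does not demand one table per drug. That is true, so a single table of events related to any study treatment would satisfy it. A table limited to eltrombopag does not.
3. **Section 4 is a weak yardstick.** In both plans it lists only added efficacy endpoints; the primary-analysis SAP recorded its removal of relative dose intensity in the document history instead. That is fair, but the final SAP's history does not record this removal either.
4. **No conclusion changes.** The trial is single-arm and descriptive. Tables of all, serious, graded and by-period events, and of those leading to discontinuation or dose change, remain. This stands, and it is why the point is minor.

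**Conclusion.** The concern holds, at minor severity. What is missing is a cumulative update, at the final cut-off, of a summary that the protocol specifies and the primary-analysis SAP planned. No count of participants or events is claimed, because the documents give none.

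r-ATG attribution should be essentially complete by the primary cut-off, since dosing ends on Day 5. The practical loss is therefore mostly events attributed to CsA alone in responders, between the primary cut-off and 30 days after their last eltrombopag dose. CsA exposure after that point would stay outside the table even once it is restored.

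The conclusion rests on reading study treatment as the protocol and the final SAP both define it. It does not depend on the accrual assumptions, which only bound the size.

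**What to change.** In Section 2.8.1 of the final-analysis SAP, put CsA and r-ATG back beside eltrombopag in the relationship summary, as the primary-analysis SAP has it. The minimum that meets Protocol 12.5.2 is to add one table of treatment-emergent events related to any study treatment. If the sponsor prefers to leave it out, Section 4 should declare and justify the removal.

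The cost is one phrase and one re-run of a table already specified for the primary analysis, using causality data already collected. No new data, derivation or protocol amendment is needed.
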